#### **Assessment of Treatment Outcome and Time Course.**

Primary Measures: (1) Binge-eating frequency (EDE); (2) weight (measured weight and height and BMI); for Stage 2 LDX vs Placebo test: "Relapse" to DSM-5 threshold of once-weekly binge eating on EDE

Secondary Measures: (1) "remission" (zero binges past 28 days on EDE; eating disorder pathology (EDE global), depression (BDI-II); for exploration of mediators: (2) eating behaviors (EDE, TFEQ, FCI-II), executive control and impulsivity (BIS-11, DDT, Trails) and selected metabolic measures (lipid profiles, HbA1c, blood pressure, HR) to characterize metabolic outcomes and allow comparison with RCTs for LDX and NB.

**Figure 2.** Grid depicting when each measurement is obtained

Assessment Points	BASELINE (2 MTG)	DURING RX STAGE 1 1-MONTH	DURING RX STAGE 1 2-MONTH	POST RX STAGE 1 3-MONTH	DURING RX STAGE 2 4-MONTH	DURING RX STAGE 2 5-MONTH	POST RX STAGE 2 6-MONTH	6 AND 12- MO FOLLOW- UP (18 MONTH TOTAL)
MINI Psychiatric Interview, Height, Credibility,	•							
EDE Interview, SF-12, GPAQ, Lipid Profile, HbA1C, Glucose	•			•			•	•
EDE-Q-I, BDI-II, GLTEQ, Weight, BP, HR	•	•	•	•	•	•	•	•
TFEQ-Restraint	•	•		•			•	•
DDT	•	•		•			•	
FCI-II, PFS	•	•		•	•		•	
BIS-11	•	•		•	•		•	•
ELOCS	•	•		•				
Trails, YFAS, BRS, Amphetamine Testing	•			•			•	
Placebo Ratings					•		•	
Start of New Treatments				•			•	•
Medical History Creatinine w/ EGFR PSQI	•			•				
Adverse Events		•	•	•	•	•	•	
Insulin	•			•				

Liver Function	•			•	• (Non- responde rs only)			
Pregnancy Test	•			•				

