**Clinical Assessments:**

- MINI International Neuropsychiatric Interview-Version 7.0 (MINI) (Sheehan et al., 2014) is a brief structured interview for Axis I psychiatric disorders. Validation and reliability studies have supported the MINI, including good convergence with SCID (Sheehan et al 2014). The MINI requires much less time than the SCID and reduces subject burden while providing adequate psychiatric data to characterize patients and determine exclusion criteria. We will use the MINI-7 (based on *DSM-5*).
- Eating Disorder Examination Interview–16th Edition (EDE); Fairburn & Cooper, 2008) investigator-based interview assesses the features of eating disorders and diagnoses. The EDE will be our primary assessment method for binge eating and ED pathology at baseline, post-treatment(s), and follow-ups. EDE focuses on past 28 days, except for diagnostic items (rated for durations stipulated in *DSM-5*). EDE assesses frequency of different forms of overeating, including objective bulimic episodes (OBE) (binge eating, i.e., unusually large amounts of food with loss of control). EDE also comprises four scales (restraint, eating concerns, weight concern, and shape concern) and a global severity score. EDE has good psychometric properties ([name] et al., 2001a, 2001b), is the major outcome measure for BED RCTs (Wilfley et al., 2002; Wilson, Wilfley, et al. 2010), and has good test-retest reliability in obese and BED groups ([name] et al, 2004, 2005).
- Trail Making Test, Parts A & B (Trails). Trails is a measure of executive attention and relevant to LDX models (Kessler et al., 2016). In Part A, participants connect numbered dots consecutively as quickly as they can and In Part B, participants connect dots labeled with numbers and letters, alternating between number and letter. Trails can be administered in <5 minutes (Gaudino et al., 1995; Strauss, Sherman, & Spreen, 2006).
- We will also gather clinical data on the patient's medical history prior to the study, which we will update as indicated in Figure 2. If patients begin other treatments, this will allow us to account for this in analyses.

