**Self-Report Questionnaires:**

- EDE-Questionnaire Version with Instructions (EDE-Q-I); Fairburn & Beglin 1994; Celio, Wilfley et al. 2004) generates the same eating data and scale scores as EDE interview, has good test-retest reliability with BED ([name], Masheb et al. 2001; Reas, [name] et al. 2006). EDEQ will be used across all assessment points given its low burden (in addition to EDE at major assessment points). EDEQ converges well with EDE as a measure of "change" (Sysko, et al. 2005). In N=200 BED patients, alphas for the four scales ranged .71 to .75.
- Three Factor Eating Questionnaire (TFEQ); Stunkard & Messick, 1985) taps eating behaviors with 3 factors: cognitive restraint, disinhibition, and hunger; however, we will be using the restraint subscale for this study. TFEQ has validity (Foster et al., 1998), and shows differential response across treatments consistent with putative CBT mechanisms (Blomquist & [name], 2011; [name] & Masheb, 2005; Safer et al., 2004). In N=200 BED patients, alphas for the 3 scales ranged .67 to .76.
- Food Craving Inventory (FCI-II); White et al., 2002) assesses general and specific food cravings (relevant for NB) and comprises 4 subscales for different food groups. FCI-II is validated and

psychometrically supported in studies with obese and with BED groups (White et al., 2002; White & [name], 2005). Internal consistency was 0.93 for total score and ranged 0.70-0.85 for subscale items in N=464 BED patients.

- The Power of Food Scale (PFS) (Lowe et al., 2009) assesses psychological impact of and drive to eat palatable foods. PFS measures appetite for – rather than consumption of – palatable foods. PFS has been validated in normative (Lowe et al., 2009) and treatment-seeking obese patients (Cappelleri et al., 2009). PFS comprises 3 scales reflecting food proximity (food available, food present, and food tasted) supported by factor analysis and good test-retest reliability and internal consistency (range 0.81-0.91) (Cappelleri et al., 2009). The PFS is a good measure of the hedonic impact of food environment cues; fMRI studies have reported associations with state cravings for desired foods and shifts in brain networks (Rejeski et al., 2012).

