### DATA ANALYSIS

Baseline demographic and clinical characteristics for randomized groups will be compared using chi-square tests for categorical variables, and ANOVA or Kruskal-Wallis tests for continuous variables. Continuous variables will be examined for adherence to normal distribution using normal probability plots and Kolmogorov-Smirnov tests. If normality not satisfied and transformations do not help with achieving normality, alternative analytic strategies will be considered such as generalized estimating equations or nonparametric methods. Dropouts and completers will be compared. Analyses will be intent-to-treat; patients will be followed regardless of treatment completion to minimize missing data. Primary outcomes will be tested at two-sided 0.05 significance level. Secondary analyses will be adjusted for multiple tests using Bonferroni correction.

Overall Data Analysis Strategy will involve MIXED EFFECTS MODELS (Diggle et al, 2002, Gueorguieva & Krystal, 2004) to compare treatments. These models allow for different numbers of observations per subject, use all available data on each subject, and are unaffected by randomly missing data. Further advantage is capacity to test and account for individual-difference contributions to treatment outcomes (Cudeck, 1996; Cudeck & Klebe, 2002; Hedeker et al., 1996; Hedeker & Gibbons, 1996; Singer, 1998). They provide flexibility in modeling the correlation structure of data. In models for each outcome, we will include fixed effects of time, treatment, and interaction between time and treatment, and random subject-level effects. Because we cannot a priori predict the shape of responses over time in each arm of the trial we will first treat time as a categorical predictor and will then test for polynomial trends over time. We will consider different error structures (e.g., AR1, independence) and select the best fitting one based on information criteria. We will

compare dropout patterns between groups and if there are concerns of informative dropout or informative intermittent missing data, we will use pattern mixture models (Hedeker & Gibbons, 1997) to perform sensitivity analyses.

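### Stage 1 binge eating (EDE) has a single post-baseline visit, so the planned mixed model covers dropout related only to arm and baseline; the monthly EDE-Q-I could extend that cover and has no role in this analysis

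*Combined protocol and SAP*

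**What the plan says.** Assessment of Treatment Outcome and Time Course names EDE binge-eating frequency as a primary measure. Clinical Assessments states: "The EDE will be our primary assessment method for binge eating and ED pathology at baseline, post-treatment(s), and follow-ups". In Figure 2 the row "EDE Interview, SF-12, GPAQ, Lipid Profile, HbA1C, Glucose" is marked at baseline, month 3, month 6 and the follow-ups, and is blank at months 1 and 2. The row "EDE-Q-I, BDI-II, GLTEQ, Weight, BP, HR" is marked at every visit. Self-Report Questionnaires says of the EDE-Q-I that it "generates the same eating data and scale scores as EDE interview" and that "EDEQ will be used across all assessment points given its low burden".

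The Stage 1 paragraph for Aims 1 and 2a sends both co-primaries to the overall mixed-model strategy: time as categorical, then polynomial trends, with the error structure chosen by information criteria. The stated protection is that such models "use all available data on each subject, and are unaffected by randomly missing data". Pattern-mixture models are added as sensitivity analyses "if there are concerns of informative dropout or informative intermittent missing data". No identifying restriction or delta is given. The Aim 2b text uses repeated EDE-Q-I measures for exploratory mediation.

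**The concern.** A mixed model gains its protection against dropout from outcome values observed before the participant leaves. For Stage 1 EDE there are none after baseline. If early response influences who is missing at month 3, that missingness is not random as far as this model is concerned, because early response is not in the model. The same information is collected in every arm at months 1 and 2 through the EDE-Q-I.

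CBT versus LDX on binge eating is one of the primary hypotheses. The plan's own expectations make an arm difference plausible: the Aim 2b text expects people without a rapid response to improve no further on LDX but to go on improving gradually on CBT. Early response would then predict the month-3 value differently in the two arms. The co-primary weight outcome does not share the problem, because weight is measured at every visit.

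**Working it through.** **1. The plan's power figure.** Inputs from Power Analysis: 60 per arm, up to 20% dropout, d = 0.64, two-sided alpha 0.025. Then n = 60 × 0.80 = 48 per arm. Normal approximation: power = Φ(d√(n/2) − z₀.₉₈₇₅) = Φ(0.64 × √24 − 2.241) = Φ(0.894) = 81.4%. The two-sample t version gives 80.3%. The stated figure of more than 80% is reproduced. It allows for lost precision, not for bias.

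**2. What the two-visit model gains from dropouts.** Simulation with 60 per arm, 20% missing completely at random and an assumed baseline to month-3 correlation of 0.6:

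| Data used | Time × arm estimate | SE |
|---|---|---|
| All participants | 0.639 | 0.179 |
| Completers only | 0.641 | 0.183 |

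The baseline-only participants add almost nothing.

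**3. Identification of the pattern-mixture model.** Two patterns (completer, dropout) × 3 arms × 2 times = 12 coefficients. The dropout pattern has no month-3 EDE in any of the 3 arms, so the design has rank 12 − 3 = 9. The three dropout time effects need an outside assumption. With a monthly measure and a linear trend the rank is 12 of 12, although the dropouts' month-3 value is then an extrapolation.

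**4. Size of bias.** Assumptions not in the documents: outcome SD 1; adjacent-month correlation 0.7; EDE to EDE-Q-I correlation 0.5–0.9; dropout log-odds slope 0.5–2 per SD of month-2 EDE-Q-I. Absolute bias in the two-arm contrast, in SD:

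| Dropout in the two arms | Dependence in one arm only | Same dependence in both |
|---|---|---|
| 20% / 20% | 0.02–0.14 | about 0 |
| 30% / 10% | 0.04–0.20 | 0.03–0.12 |

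Adding EDE-Q-I months 1 and 2 brings every entry to within 0.011 of zero.

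The zero for a shared mechanism also needs equal early-to-late correlation. In a second simulation both arms had the same mechanism and 20% dropout (slope 1, baseline correlation 0.3), but the month-2 to month-3 correlation was 0.7 in LDX and 0.3 in CBT. A true 0.64 was then estimated as 0.57. At correlations of 0.8 and 0.2 it was estimated as 0.54. Adding EDE-Q-I restored 0.64 in both.

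**5. Effect on power if the bias reduces the contrast** (t-test, 48 per arm, alpha 0.025). A bias of 0.09 leaves 0.64 − 0.09 = 0.55, power 66.2%. A bias of 0.14 leaves 0.50, power 57.0%. From the plan's anticipated 0.69–0.78, a bias of 0.14 leaves 0.55–0.64, power 66.2–80.3%.

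**6. What a delta analysis would show.** Shift in contrast = proportion missing × delta. If the 20% missing in one arm differ from what is expected of them by 0.5, 1.0 or 1.5 SD, and those missing in the other arm do not, the shift is 0.20 × 0.5 = 0.10, 0.20 or 0.30 SD.

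**The case against.** Several points on the other side stand.

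- A reader might infer that the planned methods give no protection. They do give some: the two-visit model is valid when missingness depends on arm and baseline, and a pattern-mixture analysis is possible once a restriction or delta is stated. What is missing is the specification.
- A reader might infer that the EDE-Q-I counts go unused. The Aim 2b mediation analyses use the EDE-Q-I. Its absence is from the primary and missing-data analyses.
- Stopping LDX is not the same as lacking a month-3 EDE. The plan follows patients regardless of treatment completion, pays for the post-Stage 1 assessment, and invites dropouts back for follow-up evaluations. This lowers missingness, but Power Analysis still allows up to 20% dropout, and the data monitoring text cites 20–38% attrition in earlier pharmacotherapy trials.
- It would be wrong to say that the plan could not notice a problem. It compares dropout patterns between groups and reviews differential dropout. Those checks can flag unequal rates. Equal rates with different reasons are harder to see, and noticing either does not correct the estimate.
- The sizes rest on assumed values. Selective loss of poor responders from LDX alone would work against the hypothesis that CBT is better, so its cost there would be power rather than a false positive.
- The polynomial and error-structure steps have no content with two EDE visits. That is editorial: the strategy is written for all outcomes, and leaving the steps in biases nothing.
- Assessment Procedures calls months 1 and 2 major assessments, and the EDE-Q-I text places the EDE at major assessment points. Figure 2 and Clinical Assessments are more specific and show no EDE then.

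**Conclusion.** The point holds as a gap in specification that is cheap to close. For Stage 1 EDE binge eating, the claimed robustness to random missingness reduces to missingness explained by arm and baseline. The named sensitivity analysis cannot be run as written, and relevant data already collected are left out of both. The plausible bias is about 0.02–0.14 SD at 20% dropout per arm when early response drives dropout in one arm only. It is about zero when mechanism, rate and early-to-late correlation are the same in both arms. The documents fix neither its direction nor its size, so they do not support a claim that the contrast will be biased, or that the trial is underpowered for this reason.

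**What to change.** In the Stage 1 analysis text:

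1. State that the EDE binge-eating model uses baseline and month 3.
2. Impute missing month-3 EDE by multiple imputation within arm, with the month-1, month-2 and (if present) month-3 EDE-Q-I binge counts and monthly weight as auxiliary variables. Modelling EDE and EDE-Q-I jointly is an alternative.
3. For this outcome, replace the unidentified pattern-mixture check with a delta-adjusted version of that imputation, with the range of deltas fixed in advance and allowed to differ by arm.
4. Align the wording on major assessments with Figure 2.

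The cost is plan wording and modest programming; no visits, data or participants are added. The method relies on the association between EDE-Q-I and EDE, which can be estimated from paired baseline and month-3 values. It gives little protection for people lost before month 1, who have no post-baseline EDE-Q-I. When half the dropout was assumed to occur before month 1 and to be driven by unobserved status, adding the EDE-Q-I removed only about half the bias: 0.58 and 0.55 became 0.61 and 0.60, against a true 0.64. For those participants the delta analysis is the safeguard.

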**Randomization to Stage 1 Treatment.** Eligible participants who provide written informed consent will be randomized in equal proportions to one of three treatments (blocked randomization with random block sizes of 3 and 6 for Stage 1 to obviate any secular trends). Randomization will be stratified by two variables to be tested as moderators (overvaluation of shape/weight (based on  $\geq 4$  EDE item scores) and depression (based on  $> 16$  BDI-II score) ([name], Masheb, Crosby, 2012).

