**Randomization to Stage 2 Treatments for LDX and CBT+LDX (Stage 1) “Responders”.**

“Responders” to Stage 1 LDX (i.e., LDX and CBT+LDX) treatments will be defined as 65% or greater reduction in binge-eating. This cut-point is based on reliable findings regarding prognostic significance of such reductions ([name] et al., 2006; 2012) and supported by recent report on “time course of the effects of LDX” (McElroy et al., 2017). “Responders” will be randomized in equal proportions (using stratified blocked randomization with Stage 1 treatment as a stratifying variable) to LDX or placebo (double-blind) for 12 weeks.

**CBT Treatment Protocol.** CBT will be delivered by trained and monitored research clinicians following manualized protocols we have used successfully in previous RCTs (e.g., [name] et al., 2005, [name] et al., 2011). CBT will be delivered in individual sessions weekly for 12 weeks following CBT manuals based on Fairburn et al (1993) used in our RCTs ([name] et al., 2005, 2011) which are similar to those used in major RCTs testing CBT delivered via 12-24 weeks (Wilfley et al., 2002; Wilson et al., 2010). The CBT manuals provide detailing session-by-session procedures for clinicians and parallel guides are provided to the patients to facilitate homework and mastery of the material. CBT, a specialist focal treatment, consists of

three overlapping phases. Phase one involves establishing a collaborative therapeutic relationship while focusing on educating the patient about the nature of binge-eating and factors thought to maintain the problem. Specific behavioral strategies (e.g., self-monitoring) are used to help patients identify problematic eating patterns while establishing a normal structured eating pattern. Phase two integrates cognitive restructuring procedures, where patients learn to identify and challenge maladaptive cognitions regarding eating and weight/shape and thoughts that trigger binge-eating. Phase three focuses on maintenance of change and relapse prevention.

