(1) **STAGE 1 – Primary Outcomes Aim 1 and Secondary Outcomes Aim 2a:** Compare LDX and CBT effects, alone and in combination, for acute BED outcomes. Analyses examining the co-primary outcomes (reduction in binge-eating and percent weight loss) and examining the secondary outcomes (binge remission, eating disorder psychopathology, depression, metabolic variables) will be intent-to-treat using mixed-effects models per the overall strategy described above. Mixed-model analyses on continuous (or pseudo-continuous) data will use SAS PROC MIXED; mixed-model analyses on binary variables will use SAS PROC GLIMMIX. Logistic regression will be used for categorical outcomes (i.e., remission from binge-eating (defined as 0 binges/past 28 days on EDE interview). Significantly greater reductions in binge eating in CBT and CBT+LDX groups compared to LDX, and weight loss in LDX and CBT+LDX compared to CBT will be considered supportive of our primary aim hypotheses. We do not anticipate significant differences between CBT and CBT+LDX on binge eating and between LDX and CBT+LDX on weight loss but the mixed model approach will allow us to estimate the magnitude of the effects with associated confidence intervals.

(2) **STAGE 1 – Secondary Outcomes Aim 2b:** Explore conceptually and empirically supported predictors, moderators, and mediators for the primary outcomes (reductions in binge-eating and weight loss) and secondary categorical outcome (binge-eating remission). We will use the Kraemer et al (2002) approach to assess predictor, moderator and mediator effects by adding potential predictor, moderator and mediator variables to the models above. Predictors will be identified as variables with significant main effects on the outcome, moderators as variables with significant interactions with treatment on the outcome, and mediators will need to be significantly affected by treatment, to be related to the outcome and have main or interactive effects with treatment on the outcome. We will explore two empirically-supported predictors and moderators of BED outcomes – overvaluation of shape/weight (EDE) and depression (BDI-II) ([name], Masheb et al., 2012; [name] et al., 2013). It is necessary to test previous findings to establish them specifically for CBT and LDX treatments to inform prescription (i.e., for whom these “leading” treatments work best).

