analytic strategy of studies testing medication for maintenance (i.e., fluoxetine) for bulimia nervosa (Romano et al (2002) and for anorexia nervosa (Walsh et al (2006) which was recently used in the Shire maintenance study of LDX for BED (Hudson et al., 2015). Stage 2 LDX and placebo will be compared on the proportion of Stage 1 responders who “relapse” using chi-squared tests and Cox Proportion Hazards Tests; we will explore further using survival analyses to estimate whether time to relapse differs between LDX and placebo. For the secondary outcomes, we will use mixed effects models to assess whether there is significant change in binge eating or weight loss between the group who continue LDX treatment and the group who receive placebo. We anticipate that subjects randomized to LDX maintenance will maintain better outcomes than patients randomized to placebo. We will also perform parallel analyses on all three groups (CBT, LDX, CBT+LDX) to compare outcomes at the 6-month time point (i.e., comparing 3-month CBT and 6-month two-stage treatments).

(4a) **STAGE 2 – Secondary Aim 1:** Explore LDX and CBT effects, alone and in combination, for longer-term BED outcomes. Our two-stage design will also allow us to also compare CBT (i.e., Stage 1 CBT-only short-term) versus the Stage 2 LDX/placebo maintenance treatment (i.e., Stage 2 LDX/placebo following Stage 1 LDX or Stage 1 CBT+LDX) for longer-term outcomes through 18 months. This will inform clinical questions regarding whether LDX maintenance treatment following either acute LDX treatment or acute combined CBT+LDX differ and whether it offers any additional benefits over acute CBT-only (4b).

**STAGE 2 – Secondary Aim 2:** Among Non-responders to Stage 1 treatments with LDX, Explore the effectiveness of switching to an alternative medication (NB versus placebo). Primary outcomes will be reducing binge-eating and reducing weight and secondary outcomes will be binge-eating remission, eating-disorder pathology, and depression. We will use similar analyses to Primary Aim 1: mixed models for the continuous outcome variables and logistic regression for categorical (remission) variable.

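### The Stage 1 primary model leaves out the randomisation strata and baseline EDE binge eating as covariates, and the Stage 2 relapse tests name no stratum: a missed gain in efficiency, not an error of validity

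*Combined protocol and SAP*

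**What the plan says.** Section 13, Overall Data Analysis Strategy, lists the terms for each outcome: "we will include fixed effects of time, treatment, and interaction between time and treatment, and random subject-level effects". Item (1) sends the "co-primary outcomes (reduction in binge-eating and percent weight loss") to that strategy. If assumptions fail, "If normality not satisfied and transformations do not help with achieving normality, alternative analytic strategies will be considered".

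Under Randomization to Stage 1 Treatment: "Randomization will be stratified by two variables to be tested as moderators". These are overvaluation (EDE item score of at least 4) and depression (BDI-II above 16). They enter the analysis only in exploratory item (2), "by adding potential predictor, moderator and mediator variables to the models above", so they are not already in the primary models.

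Stage 2 responders are randomised "using stratified blocked randomization with Stage 1 treatment as a stratifying variable". Item (3) compares relapse "using chi-squared tests and Cox Proportion Hazards Tests" and names no stratum. It says that it follows the "analytic strategy of studies testing medication for maintenance" in other eating disorders, but does not describe that strategy.

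The EDE is the primary binge-eating measure. In Figure 2 it has two values within Stage 1: baseline and month 3.

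**The concern.** An analysis normally reflects the restrictions placed on the randomisation, and a baseline measure of the outcome is usually the most useful covariate available. The plan calls overvaluation and depression empirically supported predictors of outcome. That is the condition under which leaving them out makes the tests conservative.

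For EDE binge eating the plan also leaves the primary contrast open. With two EDE values in Stage 1, a time-by-treatment term needs baseline as a level of time and most plausibly amounts to a change-from-baseline comparison. This is inferred from the schedule and from the outcome being a reduction; it is not stated. The other reading is that the month-3 group difference is tested. Baseline is not a covariate under either.

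At stake is precision on the co-primary with the smaller expected effect: d = 0.69 to 0.78 for binge eating, against 1.53 for weight.

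**Working it through.** **1. The plan's own figure.** From POWER ANALYSIS: 60 per arm, 20% dropout, d = 0.64, two-sided alpha 0.025. Analysed n = 60 × 0.8 = 48 per arm, z = 2.2414.

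Power = Φ(0.64 × √(48/2) − 2.2414) = Φ(3.135 − 2.241) = 81.4% (noncentral t, 94 df: 80.3%).

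This agrees with the stated more than 80%. It is a plain two-group calculation with no covariate.

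**2. Variance of each contrast.** Set the baseline SD to 1, the month-3 SD to k, and the baseline to month-3 correlation to r. Both r and k are assumptions.

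- Change from baseline: 1 + k² − 2rk
- Month 3 only: k²
- Month 3 adjusted for baseline: k²(1 − r²)

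In large samples the adjusted variance never exceeds either of the others. It equals the change-score variance only when rk = 1, and the month-3 variance only when r = 0.

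**3. Power after adjustment.** Φ(0.64 × √24 / √ratio − 2.2414), where ratio is adjusted over unadjusted variance and d is in SD units of the contrast tested. Example at k = 1, r = 0.5: Φ(3.135/√0.75 − 2.241) = Φ(1.379) = 92%. For k = 1, starting from 81%:

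| r | Ratio, change contrast | Power | Ratio, month-3 contrast | Power |
|---|---|---|---|---|
| 0.1 | 0.55 | 98% | 0.99 | 82% |
| 0.3 | 0.65 | 95% | 0.91 | 85% |
| 0.5 | 0.75 | 92% | 0.75 | 92% |
| 0.7 | 0.85 | 88% | 0.51 | 98% |

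For the change contrast at r = 0.3, 0.5, 0.7:

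- k = 0.75: ratios 0.46, 0.52, 0.56; power 99, 98, 97%.
- k = 1.25: ratios 0.78, 0.89, 0.98; power 90, 86, 82%.

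The month-3 ratio does not depend on k. If d = 0.64 is instead in month-3 SD units and the change contrast is tested (k = 1), power of 66, 81, 96% rises to 85, 92, 98%.

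**4. At alpha 0.05.** DATA ANALYSIS tests primary outcomes at two-sided 0.05, while POWER ANALYSIS uses 0.025. With z = 1.960, unadjusted power is 88% at d = 0.64, 92% at 0.69 and 97% at 0.78. For the change contrast at d = 0.78, k = 1 and r = 0.3, 0.5, 0.7, adjustment gives 99.7, 99.3, 98.6%, a gain of about 2 to 3 points.

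**5. Stage 1 strata.** Suppose they explain R² = 2, 5, 10% of the variance of the tested outcome (assumed).

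- True size of the unadjusted test: 2(1 − Φ(2.2414/√(1 − R²))) = 0.0236, 0.0215, 0.0181, against 0.025.
- Unadjusted power: Φ((3.135 − 2.241)/√(1 − R²)) = 81.7, 82.1, 82.7%.
- Adjusted power: Φ(3.135/√(1 − R²) − 2.241) = 82.3, 83.5, 85.6%.
- Gain: 0.6, 1.5, 2.9 points, possibly less once baseline is in the model.

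The form of the stratum term matters. If baseline is an unconstrained level of time, a stratum main effect adds the same constant at both visits and cancels from each participant's difference. In complete data the time-by-treatment estimate and its standard error are then unchanged. Only a stratum-by-time term lets the stratum explain variation in change.

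**6. Stage 2 relapse.** About 80 responders × 0.8 = 64, or 32 per arm; equal strata are assumed, so 16 per cell. Enumerating all 17⁴ tables, chi-squared power at 4% vs 32% is 89%, as stated. Size at nominal 0.05:

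| Null relapse in the two strata | Chi-squared | Cochran-Mantel-Haenszel |
|---|---|---|
| equal (18%) | 0.051 | 0.050 |
| 12%, 24% | 0.048 | 0.050 |
| 8%, 28% | 0.043 | 0.049 |
| 5%, 35% | 0.035 | 0.049 |

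With stratum odds ratios of 1 to 5, stratifying changes power by at most +0.8 point at 4% vs 32%, and by −0.7 to +2.8 points over the plan's other relapse pairs.

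**The case against.** The strongest reply is that nothing here is wrong. If baseline enters as the first repeated response it is not ignored, and that is a valid and common longitudinal analysis. The planned power holds without adjustment and exceeds 80% at the expected effects. Many month-3 binge counts may be zero: the background cites roughly 50 to 60% remission with CBT and 36 to 40% abstinence with LDX. The correlation r could therefore be low, and on the month-3 reading the gain at r = 0.1 is under one point. On the change reading the gain nearly vanishes when rk is close to 1, which a transformation that raises k could bring about. In Stage 2 the power change is negligible, and the cited maintenance trials may have stratified. All of this stands, and it limits the point to efficiency of uncertain size.

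It does not remove the point. One of the two contrasts gains materially at any r shown for k = 1, the plan does not say which contrast is primary, and the strategy of the cited trials is not set out here.

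A reader might go further, in three ways that the documents do not support.

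- **Inflated type I error.** Omitting prognostic strata makes the Stage 1 tests conservative; omitting non-prognostic strata costs nothing.
- **Bias.** Linear contrasts and the relapse risk difference are unbiased unless dropout depends on the strata differently by arm. In an assumed example (equal strata, dropout 10% and 30% by stratum, reversed between arms, 20% overall) completer prevalence is 0.45/0.80 = 0.5625 against 0.4375. The shift in d is 0.125 × 2√R² = 0.04, 0.06, 0.08 at R² = 2, 5, 10%. An unstratified hazard ratio is a marginal quantity slightly nearer 1, which is a different estimand and not a bias.
- **A faulty power statement.** The plan states more than 80%, and this reproduces.

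**Conclusion.** The omission is real, and the plan gives up precision from data that it already collects. For Stage 1 binge eating at d = 0.64, alpha 0.025 and k = 1, the forgone power runs from under 1 point (month-3 contrast, r = 0.1) to about 17 points (change contrast at r = 0.1, or month-3 contrast at r = 0.7). It is smaller at the expected effects and at alpha 0.05. Most of it comes from baseline EDE; the strata add about 1 to 3 points. These figures rest on assumed r, k and R² and on a normal approximation to skewed counts. In Stage 2 the case for stratifying is nominal test size and analysis as randomised, not power. The weight co-primary has little to gain, with power above 99.9% at d = 1.53. The change is worth making because it is free and settles the primary contrast in advance. The trial's conclusions would not be invalid without it.

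**What to change.** 1. **Stage 1 EDE binge eating.** Name the month-3 treatment contrast as primary and pre-specify one of two models: (a) ANCOVA with baseline EDE binge frequency and the two strata (overvaluation at least 4 or below; BDI-II above 16 or not) as covariates; or (b) a constrained-baseline mixed model with the strata and stratum-by-time terms. A stratum main effect alone is not enough in a model with baseline as a level of time.
2. **Fallback analyses.** Carry the same baseline adjustment into any transformed or GEE analysis.
3. **Percent weight loss.** Include the strata, with stratum-by-time terms if baseline is a level of time. Adjusting for baseline weight is optional.
4. **Stage 2 relapse.** Use a Cochran-Mantel-Haenszel test and a Cox model, both stratified by Stage 1 treatment.
5. **Alpha.** Reconcile 0.05 in DATA ANALYSIS with 0.025 in POWER ANALYSIS for the Stage 1 co-primaries.

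The cost is SAP wording only. Every variable is already collected, and the sample size does not change.
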